### 3.4.2 Imputation Rules for Epilepsy Onset Date

To calculate duration of seizure history, the incomplete epilepsy onset date will be imputed as following.

- Completely missing epilepsy onset date (UNK-UNK-UNK) will not be imputed, and hence no duration of seizure history will be calculated.
- If epilepsy onset date recoded as yyyy-UNK-UNK, then epilepsy onset date will be imputed as yyyy-07-01. July 1 will be used for unknown month and date.
- If epilepsy onset date recoded as yyyy-MM-UNK, then epilepsy onset date will be imputed as yyyy-MM-15. 15 will be used for unknown onset data.

### 3.5 Protocol Deviations

Listing for all protocol deviations will be provided.

Listing for major deviations that result in excluding from the PP population will also be provided for blinded phase.

### 3.6 Key Data Items

#### Study Analysis Population Definition:

- Intend-To-Treat (ITT) population: All subjects who have seizure events and received study drug.
- Modified Intend-to-Treat (mITT) population: All ITT subjects have had at least one efficacy evaluation after study drug dosed
- Per-Protocol (PP) population: All ITT subjects without any major protocol deviations.
- PK Population: All ITT subjects who provided at least one PK data point.
- Safety Population: All ITT subjects who receive at least one dose of study drug.

#### Important Derived Variables:

- Age (year) = (Screening Date – Date of Birth +1)/365.25.
- Duration of Seizure History (year) = (Screening Date – Epilepsy Onset Date +1)/365.25.
- Prior Medications and Treatments: the medications and treatments started before enrolled to the study without any change after the enrollment.
- Concomitant Medication and Treatments: the medications and treatments started on or after the time of the first dose of the study drug. Any medications and treatments started before but changed after the first dose of the study drug will be considered as concomitant medications and treatments.

- Baseline: All clinical measurements (safety and efficacy data) collected at Day 1 or before the first dose will be analyzed as baseline.
- Post Baseline: All clinical measurements (safety and efficacy data) collected after the first dose will be analyzed as post baseline.
- Treatment emergent Adverse Events (TEAE): Any AEs started on or after the time of the first study drug dosed.

**Flags for Efficacy Endpoints:**

- Treatment Response Flag  
= 'Yes', if treated seizure stopped within 2 minutes and there are no seizure events within 2 hours (120 minutes);  
= 'No', otherwise;
- Secondary Generalization Flag  
= 'Yes', if at least one post-treatment seizure event was categorized as "a complex partial seizure" or "partial seizures evolving to secondarily generalized seizures" and/or "a generalized tonic-clonic seizure";  
= 'No', otherwise;
- Number of Post-Treatment Seizures
  - a. N\_4h = # of seizures observed during 0 – 4 hours post-treatment
  - b. N\_6h = # of seizures observed during 0 – 6 hours post-treatment
  - c. N\_12h = # of seizures observed during 0 – 12 hours post-treatment
- Time to the next seizure event  
= the next seizure event start time, if the start time > 2 minutes after study drug dosed  
= censored (left censored at 2 minutes), if the start time ≤ 2 minutes after study drug dosed

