Assessment of the seizure activity is based on clinical observation by the Staff Caregiver using a stop watch. In addition, a video EEG will record the occurrence, start time, and duration, of the seizure event. PK samples will be collected 10, 30 and 60 minutes, and 2 and 6 hours after the administration of the study drug. If possible, subjects will signal when they experience a seizure event. Subject will be under video EEG surveillance throughout the Treatment Phase. The Staff Caregiver will signal the event for the video EEG recording, starts the stop watch at the time of drug administration, and mark the occurrence of the seizure event on a seizure diary. If the seizure episode does not stop within 5 minutes of the study drug administration, rescue medication other than alprazolam may be administered at the discretion of the principal investigator per the protocol of the research unit. The study exit procedures will be conducted 24 to 32 hours after the administration of study medication or when the subject discontinues from the study.

After discharge from the in-patient unit there will be a safety-follow-up phone contact 14 ±2 days after the subject received the study medication.

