8.1. Subject Inclusion Criteria

1. Subject is able to provide written, personally signed, and dated informed consent to participate in the study or will have a legally authorized representative (LAR) sign the informed consent on his or her behalf before completing any study related procedures.
2. Male or female ≥ 18 years of age.
3. Has an established diagnosis of focal or generalized epilepsy or focal and generalized epilepsy with a documented history of predictable seizure episodes that includes at least one of the following:
 - a. Generalized seizure episodes starting with a flurry of absence seizures or myoclonic seizures with a minimum duration of 5 minutes
 - b. Episodes of a prolonged focal seizure with a minimum duration of 3 minutes
 - c. Episodes of multiple (≥ 2) seizures within a 2-hour time period
4. Prior to randomization, has experienced ≥ 4 seizure episodes with predictable pattern during the last 4 weeks (qualification period) and no more than one week without a predictable seizure episode before entry into the in-patient unit.
5. Female participants (if of child-bearing potential and sexually active) and male participants (if sexually active with a partner of child-bearing potential) who agree to use a medically acceptable and effective birth control method throughout the study and for 1 week following the end of the study. Medically acceptable methods of contraception that may be used by the participant and/or his/her partner include abstinence, birth control pills or patches, diaphragm with spermicide, intrauterine device (IUD), surgical sterilization, and progestin implant or injection. Prohibited methods include: the rhythm method, withdrawal, condoms alone, or diaphragm alone.
6. Subject is able to comply by the requirements of the protocol, particularly the requirements and specific Institution policies during the in-patient stay.

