8.4. Emergency Unblinding of Treatment Assignment

In the case of a medical requirement to break the blind to determine appropriate treatment for an adverse event, unblinding of a subject's treatment assignment can be achieved through the study-specific Interactive Web Response System (IWRS). If possible, the Investigator should discuss the circumstances with the Medical Monitor prior to accessing unblinding information. In the event of a blind break, the Medical Monitor will be notified through the electronic data capture system. The subject for whom the blind is broken should be subsequently withdrawn from the study. The details regarding the process of breaking the blind are outlined in the Pharmacy Manual.

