10.3. Concomitant Medications and Procedures

All medications, including over-the-counter therapies (e.g., vitamins, herbal, and nutritional supplements), taken at the time of the Screening Visit through the Follow-Up Visit will be recorded in the subject's source documentation and documented in the eCRF.

With the exception of acetaminophen or ibuprofen for pain, ongoing doses of oral contraceptives, and stable background AEDs, medications other than study drug are not allowed from 12 hours before entry into the CRU/EMU until the end of the Treatment Phase, unless medically required.

After screening, the doses of the background AEDs should be kept stable if possible. If dose changes are deemed necessary, continued study participation of the subject should be discussed with the Medical Monitor.

Any concomitant medications taken during the Treatment Phase (up to 24 h after study drug administration), including any medication taken for the treatment of adverse events, will be recorded on the appropriate CRF. Recording of the concomitant medication will include the medication name, indication, dose, route, frequency, and time.

If a seizure episode does not stop within 5 minutes, rescue medication may be administered at the discretion of the principal investigator per the protocol of the research unit. If seizure activity continues despite use of rescue medication, the standard treatment protocol of the institution should be applied as appropriate.

In case a subject experiences respiratory distress, an inhaled short-acting beta-agonist bronchodilator should be available for use under standard dosing conditions as needed. Any concomitant medication deemed necessary for the wellbeing of the subject may be given at the discretion of the Investigator. Use of medications that are prohibited per protocol will require subject withdrawal from the study.

This document cannot be used to support any marketing authorization application and any extensions or variations thereof.

REDACTED COPY

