13.2. Endpoints

13.2.1. Efficacy

Primary efficacy endpoint:

The proportion of responders in each treatment group achieving seizure activity cessation within 2 minutes after the administration of the study drug and no recurrence of seizure activity within 2 hours.

Secondary endpoints:

- Seizure episode severity assessed by subject and/or Staff Caregiver
- Use of rescue medication
- Secondary generalization (evolution to a complex partial seizure and/or a generalized tonic-clonic seizure)

Exploratory endpoints:

- Number of seizures during the 4, 6 and 12 hour time periods after study drug administration
- Time to next seizure event with start time >2 minutes after study drug administration

Additional exploratory statistical analyses to further assess for treatment effect will be outlined in the Statistical Analysis Plan finalized prior to database lock for the Primary Efficacy Analysis.

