**Secondary endpoints:**

- Seizure episode severity assessed by subject and/or Staff Caregiver
- Use of rescue medication

- Secondary generalization (evolution to a complex partial seizure and/or a generalized tonic-clonic seizure)

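### The responder flag needs only an absence of recorded seizures, so early end of observation, or off-rule anti-seizure medication, within 2 hours can count as response

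*SAP*

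**What the plan says.** **Endpoint and flag.** Protocol 13.2.1 defines a responder as a subject "achieving seizure activity cessation within 2 minutes after the administration of the study drug and no recurrence of seizure activity within 2 hours". SAP 3.6 turns this into a flag that is Yes "if treated seizure stopped within 2 minutes and there are no seizure events within 2 hours (120 minutes") and No in every other case. Neither text mentions rescue or asks that the 2 hours be fully observed. SAP 2.2.1 lists "Use of rescue medication" as a separate secondary endpoint.

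**Rescue and other medication.** Protocol 7 states: "If the seizure episode does not stop within 5 minutes of the study drug administration, rescue medication other than alprazolam may be administered". The synopsis and SAP 1.2.2 say the same. Protocol 10.3 repeats the 5 minutes without saying when they start, and adds: "Any concomitant medication deemed necessary for the wellbeing of the subject may be given at the discretion of the Investigator".

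**Routes out of observation.** Protocol 10.3: "Use of medications that are prohibited per protocol will require subject withdrawal from the study". Protocol 8.4: "The subject for whom the blind is broken should be subsequently withdrawn from the study". Under Protocol 7, exit procedures follow at 24 to 32 hours, or when the subject discontinues.

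**Missing data and analysis set.** Protocol 13.4.2 leaves the handling of missing data to the SAP. SAP 3.4.1 deals with adverse event records and SAP 3.4.2 with the epilepsy onset date; there is nothing on the response endpoint. Under SAP 3.6, mITT, the primary analysis set, needs only one efficacy evaluation after dosing.

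**The concern.** An absence of recorded events is not the same as an observed absence of events. The flag cannot tell them apart, and its No category does not help, because a subject with nothing recorded satisfies the Yes condition first. Someone who stopped seizing by 2 minutes and left at, say, 40 minutes enters mITT and is a responder. So is someone who stopped by 2 minutes and was then given another anti-seizure drug at the investigator's discretion, with no seizure recorded up to 120 minutes. In that subject the second drug may be the reason that nothing recurred.

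This is the primary endpoint in arms of about 35, so one or two subjects matter. Without a written rule, these cases would be settled by programming or by case review, and the only response tables planned in SAP 4.1.2 (mITT and PP) would not show how the result depends on that choice.

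**Working it through.** **1. Reproduce the planned sample size.** Inputs from SAP 2.3: 57% active, 20% placebo, two-sided 0.05, 90% power. Test: chi-squared (SAP 3.3.1). The 57% is 0.3 × 50% + 0.7 × 60%. With pooled variance and no continuity correction, the mean rate is 0.385 and

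n = [1.960 × √(2 × 0.385 × 0.615) + 1.282 × √(0.57 × 0.43 + 0.20 × 0.80)]² / 0.37² = 34.2, so 35 per arm.

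The plan's figure is reproduced. Exact enumeration of the uncorrected chi-squared test at 35 per arm gives 90.7% power. The sample size is not in question.

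**2. Which subjects does the flag misplace?** Take the possible courses in turn.

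- Episode still going at 5 minutes after dosing, rescue given: fails the 2-minute test. Flag No, as it should be.
- Stopped by 2 minutes, new seizure within 120 minutes, with or without medication: fails on recurrence. Flag No.
- Stopped by 2 minutes, observation ends before 120 minutes, no seizure recorded: flag Yes, although the 2-hour status is unknown.
- Stopped by 2 minutes, anti-seizure medication given outside the rescue rule, no seizure recorded: flag Yes, although the study drug's effect can no longer be separated.

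Only the last two are open.

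**3. Size.** The documents give no count of such subjects, so the count is an assumption. One subject moves an arm by 1/35 = 2.9 points. Suppose the planned rates are the true ones and k false responders are added, so that an arm's rate rises by k/35. Exact power is then:

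| k | Placebo only | Active only | Both arms |
|---|---|---|---|
| 0 | 90.7% | 90.7% | 90.7% |
| 1 | 84.5% | 94.1% | 89.4% |
| 2 | 76.4% | 96.4% | 88.4% |
| 3 | 66.8% | 98.0% | 87.7% |

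In the active-only column the rise is not a gain: it is an inflated apparent effect.

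**4. Effect on one result.** With 20/35 against 7/35 responders, close to the planned rates, the chi-squared p-value is 0.0014. Moving active responders to non-response, with none moved on placebo, gives p = 0.012 for three, 0.039 for five and 0.068 for six. At the planned effect it takes six such subjects to lose significance; a smaller effect would be more fragile.

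**The case against.** The strongest reply is that the gap is close to empty. The dose is single, each subject has 1:1 coverage and continuous video EEG, and observation runs to 24 hours (Protocol 9.2.3, 11.5.1), so loss within 2 hours should be rare. Rescue use is tabulated for mITT and PP and listed by subject, so a rescued responder would be visible. An unobserved 2-hour status might also be read as falling under No. The first two points stand and limit the size. The third is a possible reading, but the text does not say it.

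A reader might infer more: that rescued subjects in general can be counted as responders. For clusters (inclusion criterion 3c, "Episodes of multiple (≥ 2) seizures within a 2-hour time period") the argument would be that one seizure stops by 2 minutes while the episode continues and is rescued. The documents do not support this. They use seizure, event, episode and activity interchangeably, and Protocol 11.5.1 has the Staff Caregiver record at 2 minutes whether the *episode* has ceased, which is what the rescue rule also tests. A further seizure in the cluster fails on recurrence.

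A reader might also count the unanchored 5 minutes in Protocol 10.3 from seizure onset and so place rescue inside the 2-minute window. The synopsis, Protocol 7 and SAP 1.2.2 all count from dosing. The other reading needs dosing more than 3 minutes after onset, although dosing is specified at onset, and rescue that stops the seizure within 2 minutes of dosing.

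Last, a reader might expect the false responses to gather on placebo, where rescue should be commoner. But that rescue goes to continuing seizures, which are already non-responses. Misclassification needs a seizure that stopped by 2 minutes, and an effective drug makes that group larger on active. The sign is not known.

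**Conclusion.** The point holds in limited form. As written, the flag returns Yes for two kinds of subject whose response was not established: those not observed to 120 minutes, and those given anti-seizure medication outside the rescue rule with no seizure recorded. These are separate gaps. The first is a missing-data rule that the protocol promised and the SAP does not give; the second is an unhandled intercurrent treatment.

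The number affected is unknown, probably small and possibly zero. If it is zero, power stays at 90.7%. If it is one to three, power at the planned rates could lie anywhere from 66.8% to 98.0%, depending on the arm. Those figures assume that the planned rates are true and that every added subject would really have been a non-responder, so they show sensitivity and do not predict a loss. The documents support neither a bias toward placebo nor a claim that subjects rescued under the 5-minute rule become responders.

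**What to change.** In SAP 3.6, set the flag to Yes only if all three hold, and otherwise to No:

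1. the treated seizure stopped within 2 minutes of dosing;
2. the subject was observed through 120 minutes with no seizure;
3. no rescue and no other acute anti-seizure medication beyond stable background treatment was given from dosing to 120 minutes.

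Word the primary endpoint in Protocol 13.2.1 and 13.4.2 to match, record the change in SAP 3.7 (now marked not applicable), and refer to the rule from SAP 3.4, so that the missing-data commitment is met. Keep the current flag as a sensitivity analysis. Settle this before unblinding.

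The cost is a possibly slightly lower response rate and one alignment of wording between the two documents. No new data are needed: the time of each concomitant medication in the Treatment Phase is already recorded (Protocol 10.3). This is a cheap improvement.

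Separately, the start of the 5-minute rescue period should be reconciled between Protocol 10.3, which states none, and Protocol 7 and SAP 1.2.2, which count from dosing. Which clinical rule applies is for the sponsor and investigators to decide.

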Subjects will participate in the study for up to 12 weeks, including Screening and Follow-Up. The Screening/Qualification Phase will last no more than 63 days. After that the subjects will participate in the Treatment Phase in the in-patient unit for approximately 2-8 days. Finally, there's a safety follow-up phone contact 14 days (± 2 days) after the subject received the study treatment.

Criteria for evaluation:

Efficacy:

The following will be assessed for every seizure episode and the 12-hour period following study medication administration:

Primary endpoint:

Proportion of responders in each treatment group achieving seizure activity cessation within 2 minutes after the administration of the study drug and no recurrence of seizure activity within 2 hours.

Secondary endpoints:

Seizure episode severity assessed by subject and/or Staff Caregiver

Use of rescue medication

Secondary generalization (evolution to a complex partial seizure and/or a generalized tonic-clonic seizure)

Exploratory endpoints:

Number of seizures during the 4, 6, and 12 hour time periods after study drug administration

Time to next seizure event with start time > 2 minutes after study drug administration

Pharmacokinetics:

Blood samples will be collected for plasma alprazolam concentration measurement pre-dose and at 10, 30, and 60 minutes, and 2 and 6 hours after the dosing of the study drug.

Safety:

Safety and tolerability of STAP-001 will be assessed by evaluating adverse events, vital signs, clinical laboratory and physical exams.

Sedation will also be assessed using a patient VAS.

Statistical methods:**Sample Size:**

There are no studies in the literature to provide reliable estimates of active treatment or placebo response rates. A total of 115 subjects will be enrolled in the double-blind part of the study to provide approximately 35 evaluable subjects per treatment arm [105 patients with approximately 30% of the overall study population randomized in the study being subjects with chronic daily benzodiazepines as part of their epilepsy management]. Power calculations assume a 2-sided test and significance level of 0.05 with 90% power and are based on the assumption that the proportion of responders with *STAP-001* is 57% (best active) whereas the assumed placebo responder rate is 20%.

Efficacy Analyses:

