### 3.7 Change to Planned Protocol Analysis

Not applicable.

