#### 4.1.2 Summary of Efficacy Endpoints

Table 14.2.1.1 Result of Treatment Response – mITT Population

Table 14.2.1.2 Result of Treatment Response – PP Population

Table 14.2.2.1 Results of Seizure Episode Severity Scale – mITT Population

Table 14.2.2.2 Results of Seizure Episode Severity Scale – PP Population

Table 14.2.3.1 Result of Use of Rescue Medication – mITT Population

Table 14.2.3.2 Result of Use of Rescue Medication – PP Population

Table 14.2.4.1 Result of Secondary Generalization Evolution – mITT Population

Table 14.2.4.2 Result of Secondary Generalization Evolution – PP Population

Table 14.2.5.1 Summary of Seizure Number after Study Drug Administration – mITT Population

Table 14.2.5.2 Summary of Seizure Number after Study Drug Administration – PP Population

Table 14.2.5.3 Treatment Comparison of Seizure Number after Study Drug Administration – mITT Population

Table 14.2.5.4 Treatment Comparison of Seizure Number after Study Drug Administration – PP Population

Table 14.2.6.1 Kaplan-Meier Analysis of Time to Next Seizure Event after Study Drug Administration – mITT Population

Table 14.2.6.2 Kaplan-Meier Analysis of Time to Next Seizure Event after Study Drug Administration – PP Population

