### 4.2.2 Listings of Efficacy Data

Listing 16.8.1 Clinical Response – Safety Set

Listing 16.8.2 Seizure Episode Severity Scale – Safety Set

Listing 16.8.3 Use of Rescue Medication – Safety Set

Listing 16.8.4 Secondarily Generalized Evolution – Safety Set

Listing 16.8.5 Number of Post Treatment Seizure – Safety Set

Listing 16.8.6 Post-Treatment Seizure – Safety Set

Listing 16.8.7 Time to Next Seizure Event – Safety Set

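### The Secondary Generalization flag is set by seizure type alone, so a later seizure of the same type as the treated one would be reported as evolution

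*SAP*

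**What the plan says.** Protocol 13.2.1 lists as a secondary endpoint "Secondary generalization (evolution to a complex partial seizure and/or a generalized tonic-clonic seizure", closing the parenthesis there. The synopsis and SAP 2.2.1 use the same definition.

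SAP 3.6 (Flags for Efficacy Endpoints) derives it as Yes "if at least one post-treatment seizure event was categorized as" one of three types: complex partial, partial evolving to secondarily generalized, or generalized tonic-clonic. Otherwise the flag is No. It refers neither to the seizure type at dosing nor to a time window.

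The result appears in Tables 14.2.4.1 (mITT) and 14.2.4.2 (PP), titled "Result of Secondary Generalization Evolution", and in "Listing 16.8.4 Secondarily Generalized Evolution". SAP 3.7, headed "Change to Planned Protocol Analysis", is marked not applicable.

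Two other places bear on scope:

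- The synopsis introduces the efficacy criteria with "The following will be assessed for every seizure episode and the 12-hour period following study medication administration". Protocol 13.2.1 gives this endpoint no window.
- The response flag in SAP 3.6 is Yes "if treated seizure stopped within 2 minutes and there are no seizure events within 2 hours", which separates the treated seizure from later events. The SAP also plans a separate "Listing 16.8.6 Post-Treatment Seizure".

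**The concern.** Evolution means that a seizure changes into something it was not. The flag tests only what a seizure was. Two of its three categories describe a type that can be present from onset, so a subject treated for a complex partial seizure who later has another complex partial seizure is Yes although nothing evolved.

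Such recurrences are to be expected here. Inclusion criterion 3c admits subjects because their episodes contain two or more seizures within 2 hours. Recurrence within 2 hours is already part of the primary endpoint. One of the three secondary efficacy endpoints would therefore partly re-measure the primary under another name, and the study report could offer it as separate evidence that the drug prevents evolution.

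**Working it through.** **Definition against derivation.** The endpoint text and the flag give these results:

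| Case | Endpoint (evolution) | Flag in SAP 3.6 |
|---|---|---|
| Complex partial at dosing, stops, complex partial again later as a separate episode | No | Yes |
| Focal but not complex partial at dosing, becomes tonic-clonic after dosing, nothing later | Yes | Yes only if the treated seizure counts as a post-treatment event |
| Complex partial at dosing, unchanged, nothing later | No | Yes if the treated seizure counts, No if it does not |
| Later absence or myoclonic seizure only | No | No |
| Criterion 3c cluster: focal seizure treated, tonic-clonic seizure within 2 hours | Depends on whether it belongs to the treated episode | Yes |

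The first row fails whichever way the treated seizure is counted. Rows 2 and 3 fail under opposite readings, so at most one of them applies.

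**Size.** The documents give no rate for secondary generalization or for seizure type, so there is no planned figure to reproduce for this endpoint. The only figure borrowed is 35 evaluable subjects per arm. It reproduces for the primary endpoint: 57% against 20%, two-sided 0.05, 90% power, pooled variance and no continuity correction give 35 per arm (power 90.7%). All rates below are assumptions.

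*A. Recurrence counted as evolution.* Let e be the true evolution rate, equal in both arms and fully captured. Let r be the share of the remaining subjects on placebo with a later seizure of a listed type, and r/2 the share on active. The flag reads e + (1 − e)r on placebo and e + (1 − e)r/2 on active, so the difference is (1 − e)r/2.

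- e = 0.30, r = 0.05: 0.70 × 0.025 = 0.0175, or 0.6 of 35 subjects
- e = 0.10, r = 0.05: 0.90 × 0.025 = 0.0225
- e = 0.30, r = 0.30: 0.70 × 0.15 = 0.105
- e = 0.10, r = 0.30: 0.90 × 0.15 = 0.135, or 4.7 of 35 subjects

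The drug has no effect on evolution in any of these rows.

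*B. If the treated seizure is counted by category.* Let s be the share already complex partial at dosing, assumed not to progress further. Let evolution in the rest be 30% on placebo and 10% on active. The flag reads s + (1 − s) × 0.30 against s + (1 − s) × 0.10.

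- s = 0.20: flag 44% against 28% (ratio 1.57); evolution 24% against 8% (ratio 3.0); standard error of the difference 0.1131 against 0.0855, a factor of 1.32
- s = 0.60: flag 72% against 64% (ratio 1.125); evolution 12% against 4% (ratio 3.0); standard error 0.1111 against 0.0641, a factor of 1.73

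The absolute difference is unchanged (16 and 8 points). Only the ratio and the precision suffer.

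*C. If the treated seizure is not counted.* With evolution of the treated seizure in 10% to 30% of subjects, 35 × 0.10 = 3.5 to 35 × 0.30 = 10.5 subjects per arm would not be captured as evolution.

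B and C are alternatives and must not be added.

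**The case against.** **Later seizures are in scope.** The synopsis covers every seizure episode, and under criterion 3c a later seizure within 2 hours can be part of the treated episode. A tonic-clonic seizure there may be how the episode evolved. This stands. Counting later seizures is not in itself the error, and a reader should not infer that every later seizure is miscounted. It does not rescue the flag, because evolution still needs a change of type and none is tested.

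**The case report form may settle it.** The flag's categories echo the targets in the endpoint definition, so they might be responses to a question about what the seizure became. The form and the table shells are not shown, so this can be neither confirmed nor excluded. As written, the SAP classifies events and does not refer to a starting type.

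**The flag misses evolution of the treated seizure.** A reader might infer this from the wording of the response flag and from the separate listings. Those are indirect signs, and the text does not settle the point.

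**The flag breaks a 12-hour rule.** This is also tempting, but the 12-hour scope stands only in the synopsis. The SAP's silence matches Protocol 13.2.1, so this is a point to reconcile.

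**Recurrence is reported elsewhere.** Seizure counts at 4, 6 and 12 hours and time to next seizure are planned, so a reader could see whether the flag tracks recurrence. That helps, although the SAP does not say that these summaries are split by seizure type.

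**Conclusion.** The mismatch is real and can be read directly from the text. The endpoint requires evolution, the flag does not, the outputs are titled evolution, and no change is declared. A same-type recurrence outside the treated episode is mislabelled however the treated seizure is counted. A drug effect on recurrence alone could therefore be reported as an effect on evolution.

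Size and direction cannot be derived from the documents. The 1.8 to 13.5 points in A rest on assumed evolution and recurrence rates and an assumed halving of recurrence on active. It is tempting to use the planned non-response rates (80% on placebo, 43% on active) as recurrence rates, which gives a spurious difference of up to 37 points. The documents do not support that, because non-response also includes treated seizures that did not stop within 2 minutes.

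Nor does the mix of seizure types create a systematic difference between arms, since assignment is randomized 1:1:1. The consequence is limited to one secondary endpoint for which SAP 3.3.1 names no test. The primary endpoint and the sample size are untouched. It should be corrected before lock, but it does not threaten the trial's main conclusion.

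**What to change.** Before database lock:

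1. In SAP 3.6, count as evolution only a change of the treated episode, after dosing, to a complex partial or generalized tonic-clonic seizure that was not its type at dosing. State that the treated seizure is included. For subjects qualifying under criterion 3c, state whether a later seizure within the 2-hour period belongs to the treated episode, and count it as evolution only if its type has changed.
2. Report other later seizures of the listed types on a separate line, by category, without the evolution label. State one window, reconciling the synopsis's 12 hours with the absence of a window in Protocol 13.2.1 and SAP 3.6.
3. If seizure type at dosing is not recorded, keep the current derivation. Relabel the flag, Tables 14.2.4.1 and 14.2.4.2 and Listing 16.8.4 as occurrence of these seizure types after treatment. Show treated and later seizures separately, and declare the change in SAP 3.7.

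The third step may be needed. Protocol 11.5.1 has the caregiver record only whether the seizure has stopped at 2 minutes, and Protocol 11.5.2 describes a blinded central EEG read without saying that it classifies type.

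The cost is SAP wording, a few table rows and slightly more derivation work. The evolution line will have fewer Yes events. The mITT and PP populations need not change.
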